10. STATISTICAL ANALYSIS*

Descriptive analyses (counts and proportions) will be conducted and relevant outcomes stratified by demographic group, risk behaviour and distribution pathway. Chi-squared tests will be used to assess if there are statistical differences in these outcomes according to these stratifications.

Standard deviations will be calculated for means, and interquartile ranges for medians. Also t-test and Ranksum tests will be used to see differences in means and medians across different participant groups.

Sensitivity and specificity will be calculated using standard methods with 95% confidence intervals presented using binomial approximation tests.

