3. STUDY DESIGN

3.1. DESIGN

Pilot procedures

The design is a prospective pilot implementation study. This protocol refers to both Phase 1 and Phase 2 of the pilot. Phase 1 will involve eligible individuals registering online to receive a DBS kit via post. The point of distribution and return of kits will be the NSW State Reference Laboratory for HIV, St Vincent's Hospital, Sydney.

Phase 2 of the pilot will involve more targeted distribution of kits within particular settings or populations. Site specific ethics applications will be submitted in order for phase 2 to proceed. The NSW State Reference Laboratory for HIV will remain the centralised point of DBS kit distribution and receipt, and participants will still be required to register their details online to activate the kit.

Evaluation

Evaluation of the pilot will focus on feasibility (return rate, number of DBS tests done; proportion of individuals who re-test using DBS, mode of distribution of DBS self-sampling kits); reach (characteristics of people who use the program – demographics, sexual risk behaviour and past testing history), outcomes (HIV and HCV positivity, CD4 count at diagnosis, linkage to care following a positive result); acceptability of the program among DBS kit registrants, assay test performance and cost.

These evaluation indicators will be measured from four data sources (which are detailed further in section 8):

- 1. Brief online questionnaire at registration
- 2. Follow-up call (to obtain linkage to care information)
- 3. Acceptability data collection
- 4. DBS and conventional laboratory testing results from the laboratory

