3.2. NUMBER OF PARTICIPANTS

Phase 1: Based on sample size calculations (section 9), the minimum number of participants required to determine that the program is reaching 10% or more infrequent testers (tested >2 year ago or never) than behavioural surveys is 400 gay and bisexually active men and 460 heterosexual people from CALD populations (860 in total). These individuals may undergo repeat testing and thus the total number of DBS tests, particularly in gay and bisexually active men, may be greater.

Phase 2: To accommodate Phase 2, an additional 1000 testing kits will be included, for a total of 1,860 across all population groups.

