3.3. NUMBER OF CENTRES

Phase 1: The pilot will involve centralised distribution of kits from the NSW State Reference Laboratory for HIV, St Vincent's Hospital, Sydney to individuals who register online. NSW Sexual Health Infolink (under the clinical governance of Sydney Sexual Health Centre) will be responsible for ensuring all results are delivered to participants and that participants who receive an HIV and/or HCV detected result are referred to appropriate local services.

Phase 2: Phase 2 will involve more targeted distribution of kits within particular settings defined by a set of principles outlined in the inclusion criteria described below and may include, for example, community outreach services, sex on premises venues, needle syringe program sites, and drug and alcohol services, mental health services, homelessness services, or community corrections that find it difficult to offer conventional laboratory or rapid HIV and/or HCV testing. The NSW Self-Sampling

Dried Blood Spot HIV Testing Pilot Program Steering Committee will provide advice to the Principal Investigators on which sites should be part of Phase 2 of implementation. Services will also have the opportunity to submit an Expression of Interest to the DBS Project Co-ordinator, for inclusion in Phase 2.

Site specific ethics applications will be submitted in order for Phase 2 to proceed at sites wanting to implement DBS testing into the existing service. As in Phase 1, the NSW State Reference Laboratory for HIV will remain the centralised point of DBS kit distribution and receipt, and all participants receiving a kit within specific settings will be required to register their details online to activate the kit.

Selected sites may wish to participate by promoting DBS only. This may include the placement of DBS promotional materials within the site for clients to see. In Phase 2 this may also include the positioning of DBS testing kits for eligible populations to pick-up and take home to register. These sites will not be required to submit a site-specific ethics application but will be considered a distribution point ONLY.

Overall governance for Phase 2 of the pilot will remain with NSW Sexual Health Infolink (SHIL)/Sydney Sexual Health Centre, with local clinical governance provided by the Local Health District within which each particular setting/site is located.

The expected number of sites for Phase 2 is unknown at this stage.

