5.9. DBS TESTING KIT DISTRIBUTION PROCESS

All kits will be coded with a unique identifier and stored at the NSW State Reference Laboratory for HIV. A register of kit distribution will be kept by the Project Coordinator in order to assess uptake by distribution method and to track kits from point of distribution to point of return to the Reference Laboratory for testing and outcome of results. All kits will need to be activated by participants or assisting trained workers on the dedicated DBS website, using the allocated validation code for participants registering independently of a site, or using the DBS kit code where a trained worker is assisting the participant.

In the event of a participant attempting to register on the website a second time, while their initial testing kit remains outstanding; SHIL will delete the second registration and make contact with the participant using their preferred method of contact, to advise that the initial validation code remains valid.

The DBS HIV testing kits will be distributed via the following mechanisms:

- (i) Postal pathway (commencing in Phase 1): Individuals self-identify as being eligible for the DBS study program and complete online registration and validation code to receive a DBS testing kit posted to a nominated address, self-sample a DBS specimen and post the used kit back to the central laboratory for testing.
- (ii) Settings pathway (commencing in Phase 2): Individuals directly receive DBS HIV/HCV testing kits in selected settings. Unassisted individuals receiving kits via this pathway will be required to enter the DBS website to activate the kit and receive a validation code. Depending on the setting, individuals may be supported by staff to complete online or paper-based registration and self-sampling at the point of distribution or will need to take the kit to a preferred location to complete registration and self-sampling. If the individual is completing the DBS test with assistance from a trained worker, clinician or peer worker, a validation code is not required. Instead, the trained worker will enter the DBS kit code and their own contact details for third point of validation. Inclusion criteria for eligible settings are outlined in the appropriate section above.

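### The chi-squared test by distribution pathway ignores site clustering in the settings arm, so differences between sites can be read as a pathway effect; the size depends on a site count and an intra-site correlation that the protocol does not give

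*Protocol*

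**What the plan says.** Section 10 (and the Synopsis, under statistical considerations) plans descriptive analyses with "relevant outcomes stratified by demographic group, risk behaviour and distribution pathway". It then names the test: "Chi-squared tests will be used to assess if there are statistical differences in these outcomes according to these stratifications". No allowance for site appears in either place. The method is therefore fixed in the protocol and is not merely left to an analysis plan.

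The two pathways deliver kits differently. In the postal pathway (Section 5.9) each person registers and receives a kit at a nominated address. In the settings pathway, "Individuals directly receive DBS HIV/HCV testing kits in selected settings". What happens next varies by setting: "individuals may be supported by staff to complete online or paper-based registration and self-sampling at the point of distribution", or the kit is taken elsewhere. Section 3.1 adds that "Phase 2 of the pilot will involve more targeted distribution of kits within particular settings or populations". Section 3.3 lists very different services as examples and allows some sites to act only as pick-up points. The same section states: "The expected number of sites for Phase 2 is unknown at this stage".

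Mode of distribution is part of the primary evaluation objective (Section 2).

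**The concern.** An ordinary chi-squared test treats every kit as an independent draw with one common probability per pathway. Kits handed out by one service share that service's clients, staff help and take-home practice, so their outcomes are likely to be correlated. That correlation arises in the settings arm only. The test can then reject because a few sites are unusual, with no general difference between postal and settings distribution. The evaluation could report a pathway effect that reflects which sites happened to join.

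**Working it through.** **No plan figure to reproduce.** The protocol gives no type I error, power, ICC or site count for the pathway comparison. Its sizing figures concern infrequent testers against behavioural surveys.

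**Inputs from the protocol**
- Postal: 860. Section 3.2 gives "400 gay and bisexually active men and 460 heterosexual people from CALD populations (860 in total"). These are participants, taken here as one kit each.
- Settings: 1,000 (Section 3.2 calls them kits; Section 9 calls them tests).
- Example return rate: 59%, from the UK pilot cited in Section 1.1. It is used only in the simulations, the returned-kits check and the ICC illustration.

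**Assumed inputs**
- Two-sided 5% test.
- Equal site sizes, 5 to 100 sites.
- ICC 0.005 to 0.10.

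**Formulas**
- Kits per site: m = 1,000 / number of sites.
- Design effect, settings arm only: DE = 1 + (m − 1) × ICC.
- Variance inflation of the difference: V = (1/860 + DE/1,000) / (1/860 + 1/1,000).
- Actual type I error: 2 × [1 − Φ(1.96/√V)].

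**Worked case: 10 sites, ICC 0.05**
- m = 100, so DE = 1 + 99 × 0.05 = 5.95.
- V = (0.001163 + 0.00595) / (0.001163 + 0.001) = 3.29.
- 1.96/√3.29 = 1.08, so the actual error is about 28.0%.

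**Actual type I error, equal sites**

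| Sites | ICC 0.005 | ICC 0.01 | ICC 0.05 | ICC 0.10 |
|---|---|---|---|---|
| 5 | 10.5% | 15.7% | 40.8% | 53.9% |
| 10 | 7.7% | 10.5% | 28.0% | 40.7% |
| 20 | 6.3% | 7.7% | 18.0% | 27.8% |
| 50 | 5.5% | 6.0% | 10.2% | 15.3% |
| 100 | 5.2% | 5.5% | 7.5% | 10.0% |

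**Checks**
- Beta-binomial simulation at true proportions of 59%, 30% and 8% agrees with the formula. With 10 equal sites it gives about 10–11%, 28% and 41% at ICC 0.01, 0.05 and 0.10; with 50 equal sites, about 6%, 10% and 15%.
- With uneven site sizes the same simulation gives roughly 14–15%, 38–39% and 52–53% for 10 sites, and 7–8%, 15–16% and 25% for 50.
- If only returned kits count (59% of each arm: 507 and 590), 10 sites give about 8% at ICC 0.01 and 31% at ICC 0.10.
- A Welch-type comparison using the between-site variance held 4.9% to 5.9% in every cell simulated (5 to 40 equal sites, ICC 0.01 to 0.10, 59% return).

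**Is the ICC range reasonable?** Suppose half the settings kits come from take-home sites returning 59% and half from assisted sites. ICC is the between-site variance divided by p̄(1 − p̄). With assisted return of 80%, p̄ = 0.695 and the between-site variance is 0.105² = 0.0110, so ICC = 0.0110/0.212 ≈ 0.05. Assisted return of 70% or 90% gives about 0.01 or 0.13. The assisted rates are assumptions, but the range used above is not extreme.

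**The case against.** The strongest objection is that the error rates treat sites as draws from a wider population. Sites join through committee advice or expression of interest (Section 3.3), in a mainly descriptive pilot. If the question concerns only the sites actually used, their probabilities are fixed, the variance of the pooled settings proportion is no larger than binomial, and chi-squared is not inflated. That is correct as statistics. But mode of distribution is in the primary objective, and Section 5.3 says governance was revised to support scale-up across NSW. A pathway conclusion is meant to reach beyond the sites that joined.

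Other limits stand:
- The pathway comparison did not size the study, and no decision rule rests on its p-value.
- The pathways also differ in whom they serve and in assistance given. Allowing for clustering does not remove that.
- Section 10 speaks of relevant outcomes without listing them, and Section 7 disaggregates return rate by target population only. Testing return rate by pathway is a plausible reading, not stated text.

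Three stronger readings are tempting but unsupported:
- A reader might infer one multiplier, such as a false-positive rate two to eight times nominal. That matches 10 equal sites with ICC 0.01 to 0.10 (2.1 to 8.1 times). Over the table the factor runs from about 1.0 to 10.8, and the protocol fixes neither input.
- A reader might infer that planned binomial intervals for settings proportions are too narrow. Section 10 names such intervals only for sensitivity and specificity.
- A reader might add repeat testers, since Section 3.2 says "These individuals may undergo repeat testing and thus the total number of DBS tests, particularly in gay and bisexually active men, may be greater". Several Section 7 outcomes are defined per participant, and no simulation included repeat testing. The point is secondary and unquantified.

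**Conclusion.** The concern holds, conditionally. The protocol fixes a test that assumes independence for a comparison in which one arm is grouped by site. The direction of the error is clear when the result is generalised beyond the participating sites; its size is not determined by the documents. Under the stated assumptions it is serious with about 10 sites (about 10% to 41% at ICC 0.01 to 0.10) and moderate with 50 (about 6% to 15%). It is near nil with many small sites at low ICC, or for outcomes with few people per site, such as linkage to care among those who test positive. That the site count is unknown argues for a method that is valid whatever it turns out to be.

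**What to change.** In Section 10, and in the matching Synopsis text, replace the plain chi-squared test for outcomes compared by pathway with one that accounts for site. Two options are a site-level (Welch-type) comparison and a GEE or cluster-robust model with a small-sample correction. Only the Welch-type comparison was checked here. The correction matters because model-based robust errors are fragile with few clusters, which is where the inflation is largest. Report between-site variation beside the pathway result.

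Use the recorded site as the cluster for kits from registered sites. Treat pick-up-only points as clusters where the point of distribution is known. The kit register in Section 5.9 tracks coded kits from point of distribution, but Section 3.1 also calls the laboratory the centralised point of distribution. The protocol should therefore say whether the site is recorded for kits that people pick up and take home.

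The cost is amended wording, slightly more analysis work and wider intervals for pathway differences. No extra participants are needed. Recording the pick-up point may be a small addition if it is not already done.

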11. CONFIDENTIALITY AND STORAGE AND ARCHIVING OF STUDY DOCUMENTS*

All of the clinical data required for the DBS pilot study will be routinely recorded in secure patient management systems used by South East Sydney Local Health District (SESLHD), which provides clinical governance to SHIL. All clinic staff members within the health services participating in this pilot are bound by the terms of the following NSW Health Policy Directives which relate to confidentiality within this working environment: *Code of Conduct; Notifiable Disease Data Security and Confidentiality;* and *HIV Confidentiality: A Guide to Legal Requirements*.

A central database containing de-identified study data will be established and managed by the Project Coordinator at NSW Sexual Health Infolink/NSW Ministry of Health and the NSW State Reference Laboratory for HIV, where the research staff will collate the de-identified study data. Only the Principal Investigators, Project Coordinator or other staff nominated by the Principal Investigators will have access to this password-protected central study database. De-identified study data will be stored for 15 years after completion of the study and publication, with the intention of data being made available for potential related research projects (if feasible) during this time period. At the end of the 15 year period, electronic data will be erased and hard data will be shredded.

Identifiable patient data will be held on the password-protected local health network at SESLHD and will be accessible only by SHIL Registered Nurses and the Project Coordinator for patient care purposes. Patient medical records will be stored for a minimum of 7 years before they can be securely destroyed. Medical information on any patient returning a detectable HIV or HCV result may be kept indefinitely.

Privacy and confidentiality is mandatory at SHIL when disclosing results and other personal health information. Data presented in reports and publications will be published in aggregate form and in a manner that does not identify individuals.

12. REPORTING AND PUBLICATION

The NSW State Reference Laboratory for HIV and SHIL will be required to provide monthly reports on the number of kits distributed, activated, returned and tested; and on the positivity rate of samples by distribution pathway to the BBV & STI Unit, NSW Ministry of Health and to the Steering Committee. Final evaluation of the Program will commence in the final quarter of the last 12 month period (month 45 onwards).

The results of this study will be presented in a report for use by NSW Ministry of Health, NSW Sexual Health Infolink, Sydney Sexual Health Centre, St Vincent's Hospital Sydney, the Kirby Institute for Infection and Immunity in Society (UNSW Australia), the Centre for Social Research in Health (UNSW Australia), Local Health Districts involved in the pilot, and other peak organisations.

Analysis of data will be the responsibility of the BBV & STI Unit at the NSW Ministry of Health. All reports and papers written in relation to this pilot program will be overseen by the BBV & STI Unit in the Centre for Population Health at the Ministry with input provided by other members of the Steering Committee. Any information published or circulated to key stakeholders will be presented in aggregated form and in such a way that individuals cannot be identified. Any publication of results from this project will be approved by a person at the level of Deputy Secretary within NSW Ministry of Health; in practice, this role generally falls to the Chief Health Officer.

13. APPENDICES

APPENDIX A: DISTRIBUTION FLOWCHART

APPENDIX B: TESTING FLOWCHART MAIN STUDY

APPENDIX C: RESULTS FLOWCHART MAIN STUDY

Title	Validation of dried blood spot sampling for the detection of HCV			
	RNA: A sub-study of the NSW Dried Blood Spot Self-Sampling HIV and Hepatitis C Testing Pilot Program.			
Background and Rationale	Declines in annual HCV RNA testing and treatment is threatening Australia's ability to meet the HCV Targets outlined in the Fifth National Hepatitis C Strategy and the NSW Health Hepatitis C Strategy (2022-2025). Increasing HCV testing is hampered by diagnostic pathways requiring multiple visits and loss to follow- up, amplified in key populations, such as people who inject drugs [1]. Stigma and discrimination associated with HCV and how it was acquired can be a barrier to testing and treatment initiation [2].			
	Dried Blood Spot (DBS) as an alternative sampling and testing option has been shown to increase testing and linkage to care [3,4]. It is valuable in settings where venepuncture is not available, when venous access is poor or where other barriers to accessing services may be present. Samples are produced from finger-stick collection of capillary whole-blood (50-100 μ l) onto specialised filter paper. Once dried, samples have good stability, are easy to store and do not require cold chain transport [5,6,7]. Collection of DBS samples does not require a trained clinician and can be performed by a lay person with minimal training [5].			
	Literature on HCV DBS testing has shown an overall sensitivity of > 97% and specificity >99% for diagnostic accuracy of HCV RNA [8,9,10] and sensitivity of >96% and specificity of >99% for HCV antibody [9,11].			
	There are currently no hepatitis C serological or molecular laboratory assays available within Australia that include DBS as a registered sample type and approved by the Therapeutic Goods Administration (TGA). Therefore, the NSW DBS Pilot was implemented as a research study under the TGA Clinical Trial Notification (CTN) Scheme.			
	The DBS sample type requires validation against paired venous sample in a National Association of Testing Authorities (NATA) Australia accredited laboratory, to provide the scientific evidence required by the TGA for approval of this device in routine clinical settings.			
	This validation study aims to compare the use of capillary whole blood dried blood spots obtained via fingerstick, against the use of conventional venous plasma for HCV RNA and antibody testing. If deemed an acceptable			
	alternative method of sample collection, it is likely to increase compliance with testing and reduce the need for repeat blood			

	collection in patients who are unable to provide a venous- collected specimen, such as those with a history of drug-use and children, as well as provide access to testing to those living in remote/isolated areas where access to laboratory facilities is limited.
Study objectives	This primary objective of this sub-study is to compare the
	analytical performance of DBS as a sample type for the diagnosis
	of hepatitis C (antibody and RNA) to standard of care (venous-
Otradia da stan	collected samples).
Study design	Participants will be recruited from sites participating in the HIV
	high testing volumes
	nigh testing volumes.
	Clinic staff will identify participants and offer participation in the
	sub-study After providing consent participants complete a
	capillary blood finger-stick DBS sample and a venous blood
	sample. The paired identically labelled samples will be sent to
	the Serology & Virology Division, NSW Health Pathology,
	Randwick (SAViD NSWHP) for testing.
	Results delivery will be as per standard of care by NSW Health
	Pathology to the service ordering the tests. Participants will not
	PNA positive will be linked to standard of care to assess for HCV
	treatment eligibility.
Inclusion criteria	Inclusion criteria
for participants	Participants are eligible for inclusion if the following criteria are
	met:
	a. Provide informed consent.
	b. \geq 18 years of age.
	c. Have a risk factor for the acquisition of HCV infection
	(such as current of past injecting drug use, previous incarceration)
	OR:

	 d. Are attending a service caring for people with risk factors for the acquisition of HCV infection (e.g. drug treatment clinics, needle and syringe programs, prisons, mobile outreach services, community health services, mental health services, and homelessness services). Exclusion criteria
	Is unable or unwilling to provide informed consent or abide by the requirements of the study.
Study procedures	Enrolment visit and sample collection
	Trained healthcare providers will engage with people at risk of HCV infection to determine eligibility for participation in the study. Participants fulfilling the inclusion criteria will be asked to provide consent.
	Following informed consent, the patients will undergo collection of paired venous blood via venepuncture and capillary blood via finger-stick for dried blood spot samples. Whatman 903© Cards (Merck, Germany) with five circles will be used to collect the capillary blood via finger-stick. The five circles will need to be fully filled with blood, with the paper saturated and covering the same surface when viewed at the back of the card. A minimum of 4 fully filled circles will be accepted.
	Following air drying overnight, the card will be placed in a paper envelope, followed by a zip lock plastic specimen bag containing a desiccant sachet, and transported at room temperature to the nearest NSW Health Pathology service as per standard practice. A dedicated request form for HCV serology and RNA on the paired venous and DBS samples will accompany the specimens.
	Testing
	RNA Testing: One dried blood spot from the paper cards will be processed and tested in parallel with matched venous blood plasma for the presence of HCV RNA using the Cobas© HCV 6800/8800 assay, following the manufacturer's instructions. Invalid results will be addressed by re-testing.
	Antibody Testing: One dried blood spot from the paper card will be processed and tested in parallel with matched venous blood plasma for the presence of anti-HCV using the Alinity i Anti-HCV assay, as per manufacturer's instructions. Reactive plasma samples will be centrifuged at 10,000 g for 10 min and retested in duplicate.
	Remaining samples will be stored for the duration of the study period and may be used for quality improvement testing on other more advanced HCV antibody or RNA assays should they become available.

	Sample Workf	GW Screening of J Informed Sample co ary blood = 350µJ pd DBS ary blood = 350µJ pd DBS ary blood = 350µJ pd DBS covernight, Seal Jin sen bag, transport to RSWH# 0 RT (art5-HCV) Barriage the transport of the seal of the covernight, Seal Jin sen bag, transport to RSWH# 0 RT (art5-HCV) BBS - Planma Barriage DBS - Planma	Veroparstaure (rein. Seri Section Section Test on Alabott (enti-fitay) Ren-Reactive Ron-Reactive Bana communication Comminge Comminge Storm comminge Storm c	EDTAI At collection s At laborato At labo	tta ₩ YY	turi 903 uver cardu
